**Table 2** presents study inclusion and exclusion criteria. For inclusion, participants ages 18-65 years old must have current OUD, present in otherwise good health, be seeking opioid discontinuation at the treatment facility, self-report that they wish to become/remain abstinent without using MOUD, be willing to follow study procedures, provide informed consent and use medically-accepted highly effective contraception. An additional criterion (following informed consent) is that device use will not begin until the Clinical Opiate Withdrawal Scale (COWS [17]) total score is 13 or greater (at least moderate withdrawal); thus, a consented participant could be dis-enrolled if the latter criterion is not met. Exclusion criteria include pregnancy or lactation, serious current psychiatric disorder (schizophrenia, bipolar) or use of neuropsychiatric medications that may overlap with NET's proposed mechanisms of action (e.g. anxiolytics, antidepressants, anticonvulsants, sedating H1-receptor antihistamines, prescription or over-the-counter stimulants), need for detoxification from alcohol or benzodiazepines, past 300-day exposure to extended-release buprenorphine, certain chronic illnesses (especially seizures), unstable medical conditions, or presence of cardiac pacemaker.

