## ***Statistical analysis plan***

Sample size determination. Sample size is based on statistical power analyses for the primary hypothesis based on single primary outcome (opioid abstinence without MOUD). A conservative approach was used to preserve power with a smaller effect size than observed from prior uncontrolled, non-blinded intervention studies with the NET Device. Power analyses examined sample sizes required to detect clinically meaningful group differences between sham and active groups. This represents standardized difference between the two groups after adjusting for the effect of the covariate “duration of inpatient residence” (which is capped at 28 days). Sample size determination was carried out *via* simulation in R-software; 5000 iterations were run in which group means were generated using a mixed-effect additive model. Sample size is a function of hypothesized effect size (standardized group difference) and the sign and magnitude of the regression coefficient (duration of inpatient residence). With projected N=100 (enrolled) there will be sufficient power to detect a standardized effect size of 0.45 or higher.

Missing data. In this ITT design, a participant is “included” (becomes part of the evaluable ITT data set) when he/she completes 1-hr of device use. We expect only 5% attrition, i.e. for 100 participants who complete 1-hr of device use, we expect to consent 105 individuals. A comparable trial of a

percutaneous electrical stimulation device for treating opioid withdrawal symptoms found that 71 of 73 enrolled participants completed 1-hr of device use, only 2.8% attrition [18]. **Table 1** explains how missing data are handled, i.e. for the primary efficacy endpoint, missing data are imputed as “not opioid abstinent without MOUD”. The definition of the primary endpoint (“opioid abstinence without MOUD”) and secondary endpoint (“non-opioid abstinence”) thus covers any intermittent missing values and loss to follow-up, and is not expected to impact power of the primary analysis. Premature study termination (e.g., death, relocation, or adverse events) may result in missing data, although this attrition is expected to be low. The projected sample size (N=125) was increased to cover unforeseen events.

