Participant withdrawal. Participants can withdraw from the study at any time on request. Discontinuation of device use prior to completing the minimum 1-hr treatment period constitutes withdrawal from the study. The investigator may discontinue or withdraw a participant from the study for the following reasons: (1) significant study intervention non-compliance; (2) if any clinical adverse event (AE), laboratory abnormality, or other medical condition or situation occurs such that continued participation in the study is not in the best interest of the participant; (3) disease progression which requires discontinuation of the study intervention; (4) if the participant meets an exclusion criterion (either newly developed or not previously recognized) that precludes further study participation; or (5) participant is unable to receive treatment following enrollment.

Participants who sign the informed consent form and are randomized but do not receive the study intervention will be replaced. Participants who sign the informed consent form, are randomized, receive the study intervention, and subsequently withdraw or are withdrawn, will be replaced.

Participants who withdraw from the study will receive TAU as defined by treatment staff (who are independent of the research staff), where such care may include MOUD.

Lost to follow-up. A participant is considered lost to follow-up if s/he becomes unavailable for all video assessments following discharge from the inpatient environment.

Populations for analysis. The ITT analysis dataset and the safety analysis dataset will contain all randomized participants. The per-protocol analysis dataset will contain the subset of the ITT dataset who: (1) present with a COWS score of moderate or above; (2) receive at least 1 hr treatment from the device; and (3) complete at least one post-discharge video interview.

Efficacy endpoints. The primary analysis will assume that data came from a mixed-effect linear model. Each model will include a random intercept, fixed effect for treatment, participant-specific random effect and covariate corresponding to duration of inpatient residence. The primary hypothesis involves testing the main effect for treatment difference between the groups (sham vs. active). A likelihood ratio test will examine the group effect focusing on the primary hypothesis.

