**Figure 3. Schedule of Activities**

Schedule of Activities (SoA)	Pre-Screening	Screening	Inpatient					Outpatient	
			Week -1	Week 1			Weeks 2-3	Week 4	Weeks 5-15 Week 16
Inpatient Study Day(s)		Day 1	Day 1, Baseline	Day 1, One Hour Elapsed	Days 2-7	Day 14 Day 21	Day 28 (Discharge from Site)		
Outpatient Test Weeks								OP Wk 1-11 each Day 7	OP Wk 12 Day 7
Study Site Admission		X							
Study Site Discharge							X		
End of Study									X
Informed Consent	X	X 							
Demographics		X							
Medical and Psychiatric History		MIA 							
Drug Use History		MIA 							
Physical Exam (including height and weight)		MIA 							
Vital Signs (BP, HR, RR, O2)		MIA 							
Drug Screen		MIA 					X	X	X
Contraception, Pregnancy Test, Menstrual Cycle	X						X	X	X
Drug Use Timeline Followback Interview (TLFB)								X	X
Eligibility (Inclusion/Exclusion)	X								
Contact Data	X						X		
Randomization and Stratification	X								
COWS			X 	X	X				
Administer Active/Sham Treatment (self-administration [sa])			X	sa	sa				
Opioid Craving Scale (OCS)			X	X	X	X	X	X	X
Treatment Perception (while device in use [sa])				X	sa				
Device Satisfaction Scale (while device in use [sa])				X	sa				
Device Tolerability (while device in use [sa])				X	sa				
Dass21: Depression, Anxiety and Stress			X				X		X
PANAS-SF: Positive and Negative Affect Scale (Short Form)			X	X	X				
Epworth Sleepiness Scale			X				X		X
Concomitant Medications				X	X	X	X	X	X
Adverse Events			X	X	X	X	X	X	X
Device Deficiencies				X	sa				
SF-12 Health Related Quality of Life (Short Form)							X		X

This drug screen is wider ranging to collect stratification information

Must be >13 for inclusion on Day 1

Paper (non-electronic) source data

"MIA" is Study Site Medical Intake Assessment

Notes: "OP", outpatient. "Wk", week. "sa", self-administered. "BP", blood pressure. "COWS", Clinical Opiate Withdrawal Scale, "HR", heart rate. "RR", respiration rate. "O2", oxygen saturation.

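### The ITT set is defined in two incompatible ways, and the replacement rules do not say who stays in, so the primary analysis could drop randomised participants

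*Combined protocol and SAP*

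**What the plan says.** **ITT set.** In the Statistical analysis plan, Populations for analysis puts every randomised participant in the ITT and safety datasets. Missing data says instead that a person "becomes part of the evaluable ITT data set" on completing one hour of device use. Participant withdrawal treats stopping before that hour as leaving the study.

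**Replacement.** Participant withdrawal states: "Participants who sign the informed consent form and are randomized but do not receive the study intervention will be replaced". The next sentence extends replacement to people who receive the intervention and then withdraw or are withdrawn. Neither sentence says whether the replaced person remains in the analysis.

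**COWS gate.** Participant selection criteria says that "device use will not begin until the Clinical Opiate Withdrawal Scale (COWS [17]) total score is 13 or greater", and that "a consented participant could be dis-enrolled if the latter criterion is not met". Table 2 (inclusion item 9) agrees. A footnote to Figure 3 reads "Must be >13 for inclusion on Day 1". The per-protocol set is the part of the ITT set who, among other conditions, "present with a COWS score of moderate or above".

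**Order of steps.** Figure 3 marks the row "Randomization and Stratification" to the left of the Day 1 Baseline column, where COWS first appears. Randomization and blinding has the research assistant pick the device by Study Device Number after electronic notice of inclusion.

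**Numbers.** Fifty per arm are to be randomised. Missing data expects 105 consents for 100 people completing one hour (5% attrition), and separately gives N=125 to cover unforeseen events.

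**The concern.** The two ITT definitions differ exactly where it matters: people allocated to an arm who do not reach one hour. The plan's own rationale makes that window sensitive to treatment. Study design says that prior open-label use showed benefit within about 15 to 20 minutes, and participants are told they may stop when they feel no benefit. Reaching one hour may therefore depend on the arm. Conditioning the primary analysis on it gives up the protection of randomisation.

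Replacement adds to the uncertainty. More than fifty per arm may be randomised, and the plan does not settle which of them are analysed. With two definitions available, the choice of primary set could be made after data are seen.

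If allocation also precedes the COWS gate, people who never qualify for device use would enter the randomised set. That loss could be avoided.

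**Working it through.** **1. The two definitions side by side**

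| Randomised participant | Populations for analysis | Missing data |
|---|---|---|
| Never starts the device | In; missing weeks count as not abstinent, so 0/12 | Out |
| Stops before one hour | In; 0/12 if no follow-up | Out |
| Completes one hour, later withdraws | In | In; replaced, with effect on the analysis set unstated |

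Replacement alone removes nobody from an all-randomised set. The removal comes from the one-hour rule, and the replacement text leaves unclear whether those removed are also displaced.

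**2. The plan's own figure**

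100 × (1 + 0.05) = 105, as stated; 100 / (1 − 0.05) = 105.3, rounded up to 106. The figure reproduces to within one person. It covers consent to one hour. The plan gives no rate from randomisation to one hour and no COWS-failure rate.

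**3. Dilution if everyone randomised is kept**

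Assumptions: a fraction d in each arm is untreated and scores 0/12, SD is unchanged, and all loss follows randomisation. Effect = 0.45 × (1 − d).
- d = 5% (the plan's consent-to-one-hour projection): 0.45 × 0.95 = 0.43.
- d = 2/73 = 2.7% (the comparable device study cited by the plan): 0.45 × 0.973 = 0.44.

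Power by the simple two-group formula, Φ(effect × √(n/2) − z), with alpha 0.05 assumed:
- n = 50 per arm, effect 0.45: 0.45 × √25 = 2.25. Two-sided Φ(2.25 − 1.96) = 61%; one-sided Φ(2.25 − 1.645) = 73%.
- n = 50/0.95 = 52.6 per arm, effect 0.4275: 0.4275 × √26.3 = 2.19. Two-sided 59%; one-sided 71%.

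The plan states no alpha, sidedness or numeric power, and its simulation inputs are not given. These values show only the change, about two percentage points, and do not test the sample size.

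**4. Bias if the one-hour rule is applied**

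Illustration, with assumed inputs: both arms truly average 20% abstinent weeks over all randomised, and those excluded would have scored zero. Mean among those retained = 20 / (1 − d).

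| Excluded, active | Excluded, sham | Apparent difference (active − sham) |
|---|---|---|
| 5% | 5% | 0 |
| 2% | 8% | 20.4 − 21.7 = −1.3 points |
| 0% | 10% | 20.0 − 22.2 = −2.2 points |
| 10% | 0% | 22.2 − 20.0 = +2.2 points |

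Over 12 weeks, 2.2 points is 0.022 × 12 = about 0.27 weeks. A true null can thus show a difference of either sign, depending on which arm loses more people.

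**5. Order of randomisation and COWS**

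In the text version of Figure 3 the randomisation mark falls under Pre-Screening. It may belong under Screening, because a footnote places there the drug screen that supplies the stratification information. Both columns precede Day 1 Baseline. The per-protocol COWS condition suggests that ITT members may be below the gate. No sentence states the order.

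**6. COWS threshold**

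A score of exactly 13 satisfies the text and Table 2 but not the Figure 3 footnote.

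**The case against.** **The formal definition is clear.** Populations for analysis is where analysis sets are defined, and it says all randomised. The Missing data sentence could be loose wording for an evaluable subset. That is possible, but it uses the ITT label and fixes the 100 on which sample size rests, so an analyst could follow either.

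**The ordering evidence is weak.** A reader might infer that the Schedule by itself breaks the ITT set. The documents do not establish that. The table's columns are visibly shifted in the text version; Screening is itself headed Day 1; and Figure 2, which may show the order, could not be seen. Device selection follows notice of inclusion, and the footnote ties inclusion to COWS, so COWS may already come first. Against this, Missing data uses 'included' for completing one hour, so the term has two senses and cannot settle the order. The per-protocol condition may merely restate eligibility; it is suggestive only.

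**COWS failures are not said to be replaced after allocation.** This stands. The dis-enrolment text speaks of consented people, and the replacement text does not mention COWS. Failures before device start should also be similar in both arms under blinding, costing mainly precision and block balance.

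**A 20% loss is not the plan's figure.** A reader might set 25 of 125 against the 100 and take the effect down to 0.36. The plan offers N=125 for unforeseen events, after discussing premature termination. It is not a loss rate before one hour, and that calculation has no basis in the plan.

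**Conclusion.** The concern holds as a conflict between two ITT definitions, made worse by replacement rules that do not say who remains in the analysis. If the one-hour rule is followed, randomised and even device-exposed people leave the primary analysis, and it is no longer ITT.

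The size cannot be fixed from the plan. Keeping everyone costs little: 0.45 becomes about 0.43, if the whole 5% falls after randomisation, scores 0/12 equally in both arms, and the SD is unchanged. Excluding people who stop before one hour carries the larger risk, because the loss may differ by arm and the direction of bias is not predictable.

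The Schedule is a secondary, avoidable contributor whose true order needs to be stated. Changing that order alone would not deal with people who stop before one hour, or with treated people who withdraw and are replaced.

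**What to change.** 1. Use one ITT definition in both Missing data and Populations for analysis: all randomised participants, analysed as allocated. Call the one-hour set a modified or supportive set. The existing missing-data rule already gives a primary-endpoint value to anyone without follow-up.
2. State that replacements are added and never displace a randomised participant. Report by arm the numbers randomised but untreated and the numbers stopping before one hour.
3. State that the Study Device Number is assigned only after the COWS criterion is documented on Day 1, and move the mark in Figure 3 to match. If this is already the practice, it is only a clarification.
4. Reconcile the COWS threshold between Participant selection criteria and Table 2 on one side and the Figure 3 footnote on the other.

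The cost is a protocol and SAP amendment and a site instruction. No visits are added, since the device is already selected on site from a pre-printed table. The price of the all-randomised set is the small dilution shown above.
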